#### Abbreviations

AE	Adverse Event
С	Control
CDC	Centers for Disease Control and Prevention
CFR	Code of Federal Regulations
COVID-19	Coronavirus Disease 2019
CRF	Case Report Form
CRO	Contract Research Organization
FDA	Food and Drug Administration
GCP	Good Clinical Practice
HIV	Human Immunodeficiency Virus
ID	Identification
IRB	Institutional Review Board
LIVD	Laboratory In Vitro Diagnostics
LOINC	Logical Observation Identifiers Names and Codes
QRI	Quick Reference Instructions
SAE	Serious Adverse Event
SARS-CoV-2	Severe Acute Respiratory Syndrome Coronavirus 2
SNOMED	Systematized Nomenclature of Medicine
Т	Test (detection zone)
US	United States

# **Study Synopsis**

Title	MGC Health COVID-19 & Flu A+B Home Multi Test Usability Study
Protocol Number	MGC-1001
Protocol Date	16 January 2023
Protocol Version	1.0
Study Sponsor	Medical Group Care
Study Purpose	The purpose of this study is to evaluate the usability of the MGC Health COVID-19 & Flu A+B Home Multi Test in home use.
Investigational Material/Product	The MGC Health COVID-19 & Flu A+B Home Multi Test is a lateral flow immunochromatographic antibody assay intended for the simultaneous qualitative detection and differentiation of the nucleocapsid antigen from SARS-CoV-2, influenza A and/or influenza B directly from anterior nasal swab specimens obtained from individuals, who are suspected of respiratory viral infection within five (5) days of symptom onset. This test is intended for non-prescription home use with self- collected direct anterior nares swab samples from individuals ages 14 years and older or adult lay user collected anterior nares swab samples from individuals aged 2 to 13 years.
Study Objective	The objective of the study is to determine the usability of the MGC Health COVID-19 & Flu A+B Home Multi Test in a simulated home use environment.
Study Design	This is an open label study to evaluate the usability of the MGC Health COVID-19 & Flu A+B Home Multi Test using information from the Quick Reference Instructions (QRI).
Inclusion Criteria	
 
Subjects are eligible for inclusion if the following criteria are met:         
 
An Institutional Review Board (IRB) approved informed consent / assent, if applicable, is signed and dated prior to any study related activities.
 
Male and female subjects 2 years of age and older.
 
Subject is willing to provide a self-collected nasal swab sample. (If the subject is under the age of 14, an adult lay user will collect the sample.)
 
Subject agrees to complete all aspects of the study.
 
 
 

Exclusion Criteria	
 
A subject is not eligible for inclusion if any of the following criteria apply:
 
1. Subject has a visual impairment that cannot be restored with glasses or contact lenses.
 
2. Subject has prior medical or laboratory training.
 
3. Subject uses home diagnostics, e.g., glucose meters, HIV tests.
 
4. Subject has prior knowledge of their current COVID-19 or flu infection status.
 

Target	A minimum of 30 completed subjects with a minimum of 15 subjects	
Population /	testing themselves and a minimum of 15 subjects testing another person	
Sample Size	(child 2 to 13 years old).	
Site	1 testing site in the United States	
Requirements		
Study Duration	The overall study duration is expected to be less than one (1) month, with	
Study Duration	subject participation completed in one visit of approximately one hour.	
	Primary Endpoints	
	1. Assess the usability of the Quick Reference Instructions (QRI)	
Study Endpoints	based upon observer evaluation.	
	2. Assess the usability of the kit for home use based upon subject	
	evaluation.	

# **1 INTRODUCTION**

## 1.1 Background

COVID-19 is a contagious respiratory illness, caused by infection with the novel coronavirus Severe Acute Respiratory Syndrome Coronavirus 2 (SARS-CoV-2). This communicable disease is easily transmitted through aerosolized droplets containing the infectious virus. Infections with SARS-CoV-2 can have varying degrees of signs and symptoms, ranging from asymptomatic to severe. Individuals infected with SARS-CoV-2 are believed to be contagious from as early as two days prior to symptom onset to at least ten days after the onset of symptoms.

Influenza (Flu) is a contagious respiratory illness caused by influenza viruses that infect the nose, throat, and lungs. This communicable disease is also transmitted through droplets containing the virus. Influenza (flu) can cause mild to severe illness, and at times can lead to death. There are two main types of influenza (flu) viruses: types A and B. The influenza A and B viruses that routinely spread in people (human influenza viruses) are responsible for seasonal flu epidemics each year. Individuals infected with Flu are believed to be the most contagious in the first three to four days after the onset of symptoms, however, they may still spread the virus and have no symptoms. Infants and individuals with weakened immune systems who are infected with flu viruses may be contagious for longer than seven days.

The rapid detection of infections and contacts and the implementation of infection control measures are critical for mitigation of these viruses.

The MGC Health COVID-19 & Flu A+B Home Multi Test is a lateral flow immunochromatographic antibody assay intended for the simultaneous qualitative detection and differentiation of the nucleocapsid antigen from SARS-CoV-2, influenza A and/or influenza B directly from anterior nasal swab specimens obtained from individuals, who are suspected of respiratory viral infection within five (5) days of symptom onset. This test is intended for nonprescription home use with self-collected direct anterior nares swab samples from individuals ages 14 years and older or adult lay user collected anterior nares swab samples from individuals aged 2 to 13 years.

# 1.2 Study Purpose

The purpose of this study is to evaluate the usability of MGC Health COVID-19 & Flu A+B Home Multi Test in Home Use.

# 1.3 Risk and Benefit Assessment

# 1.3.1 Potential Risks

The only study-related procedure that could impact subject safety is in the collection of nasal specimens from the anterior nares using a nasal swab. The risks of collecting a specimen using a

nasal swab may include symptoms associated with standard collection practices, such as slight pain and/or a small amount of bleeding in the nose.

All subject(s) will be de-identified using a study-specific number at the time of enrollment. All study forms, Case Report Forms (CRFs) and study samples will be labeled with the de-identified subject ID number. No identifiable patient information will be provided to Medical Group Care. No patient treatment or management decisions will be based on any results generated during this study.

Information collected for this study is confidential. However, officials of the FDA or other regulatory agencies may research records during the ordinary course of conducting their functions. A sponsor representative may also inspect research records to make certain the study data is accurate. The investigator, institution, regulatory agencies, and sponsor will protect the confidentiality of the records.

# 1.3.2 Potential Benefits

The information obtained in this study will not benefit the study subjects directly but may aid future patients by helping to rapidly and accurately detect infection caused by SARS-CoV-2, influenza A and/or influenza B.

## 1.4 Study Device Description

The MGC Health COVID-19 & Flu A+B Home Multi Test is a lateral flow immunochromatographic antibody assay intended for the simultaneous qualitative detection and differentiation of the nucleocapsid antigen from SARS-CoV-2, influenza A and/or influenza B directly from anterior nasal swab specimens obtained from individuals, who are suspected of respiratory viral infection within five (5) days of symptom onset. This test is intended for nonprescription home use with self-collected direct anterior nares swab samples from individuals ages 14 years and older or adult lay user collected anterior nares swab samples from individuals aged 2 to 13 years.

#### 1.5 Device Output

The MGC Health COVID-19 & Flu A+B Home Multi Test detects influenza A and B viral antigens and COVID-19 antigen through visual interpretation of color development on the test cassette.

Nasal swab samples are loaded into the sample port of the test cassette. The extracted specimen reacts with anti- influenza A, B and COVID-19 antibodies conjugated to colored particles and precoated onto the sample pad of the test. The mixture then migrates through the membrane by capillary action and interacts with the reagents on the membrane. If there is sufficient influenza A and/or B viral antigens or COVID-19 antigens in the specimen, a pink colored band(s) will form in the test region(s) of the membrane, i.e., COVID-19, Flu A and/or Flu B, as illustrated in Figure 1.

MGC Health COVID-19 & Flu A+B Home Multi Test Usability Study Protocol No.: MGC-1001 Version 1.0; 16 January 2023 If no color bands appear in any of the test regions, this is an indication of a negative result, as illustrated in

#### **Negative Test**

The appearance of a pink line in the control region (C) and the absence of a pink line in the test region(s) indicates a negative test result, as shown in Figure 2.

#### Figure 2.

The appearance of a colored band at the control region (C) serves as a procedural control, indicating that the proper volume of specimen has been added and membrane wicking has occurred. If the Control line (C) does not appear, as illustrated in Figure 3, the result is invalid, and the test should be repeated.

#### **Positive Test**

The appearance of a pink line in the control region (C) and a pink line in the test region(s) COVID-19, Flu A, and/or Flu B indicates a positive result for the particular viral antigen. Figure 1 depicts positive test results.

COVID-19: POS Flu A: POS Flu B: POS

Figure 1:

COVID-19: POS Flu A: POS

**Positive Results** 

COVID-19: POS Flu B: POS

COVID-19: POS

Flu A: POS Flu B: POS

Flu B: POS

Flu A: POS

SARS-CoV-2

enza A&B Combo

C

COVID-19

FluA FluB

S

#### **Negative Test**

The appearance of a pink line in the control region (C) and the absence of a pink line in the test region(s) indicates a negative test result, as shown in Figure 2.

Figure 2: Negative Result

#### **Invalid Test**

The absence of both a pink control line (C) and a pink line in the test regions or the absence of a pink control line (C) with the appearance of a pink line in the test region(s) indicates the test was invalid and must be repeated. This is illustrated in Figure 3.

Figure 3: Invalid Test Result

Invalid

Invalid

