#### 1.9 Study Design

This is an open label observational study to evaluate the usability of the MGC Health COVID-19 & Flu A+B Home Multi Test.

Each subject will be provided a MGC Health COVID-19 & Flu A+B Home Multi Test and asked to conduct the test on themselves or another subject using the Quick Reference Instructions (QRI) for the MGC Health COVID-19 & Flu A+B Home Multi Test while being monitored by an observer.

A member of the clinical study staff will observe the subject while they are conducting the test. The observer will note the completion and/or correct performance of critical steps which, if not performed correctly, could lead to an inaccurate test result.

The observer will note whether or not they agree with the subject's interpretation of the test results. A photograph of the test cartridge will be taken showing the results.

Subjects will be asked to provide their perspective on the use of the test at the end of the testing process.

In addition, a set of illustrations of test results will be provided to each subject for interpretation. Results of the testing will be used to determine whether further refinement of the QRI may be needed. The results of the testing will not be used for patient management or treatment decisions.

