# 7.1 Usability Study and Risk Mitigation for User Errors

The results will be analyzed to confirm the proper use of the QRI and usability of the MGC Health COVID-19 & Flu A+B Home Multi Test. The usability of the MGC Health COVID-19 & Flu A+B Home Multi Test will be considered valid if:

- The mean score of the subjects' response scores in the questionnaire are  $\leq 3$  for those questions with a score response between 1 and 5.
- 80% of the critical steps were performed correctly based upon the observer's assessment.
- 80% of the interpretation of the sample image results were correct.

The subject questionnaires and observer notes will be used to modify the QRI, if necessary, and additional usability testing will be conducted if needed.

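### The Section 7.1 verdict makes no use of whether subjects obtained a valid result on their own test, so usability can pass however many tests are invalid

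*Combined protocol and SAP*

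**What the plan says.** Section 1.5 (text with Figure 2) describes the control line as a procedural control, "indicating that the proper volume of specimen has been added and membrane wicking has occurred". Under its Invalid Test heading, a cassette without that line "indicates the test was invalid and must be repeated".

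The study procedure describes a single test. Section 1.9 states "Each subject will be provided a MGC Health COVID-19 & Flu A+B Home Multi Test", and Section 3.1 gives one swab, one cassette and one tube per box. Section 3.5 goes from reading the result to the photograph, the questionnaire and the ten sample images, and does not mention a repeat. The observer records agreement or disagreement with the subject's reading.

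Section 7.1 sets three conditions for a favourable verdict:

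- a mean questionnaire score of at most 3 "for those questions with a score response between 1 and 5";
- "80% of the critical steps were performed correctly", as judged by the observer;
- "80% of the interpretation of the sample image results were correct".

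The Synopsis sets the sample size: "A minimum of 30 completed subjects with a minimum of 15 subjects" testing themselves and at least 15 testing a child.

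**The concern.** The objective is to learn whether lay users can run this kit at home from the Quick Reference Instructions. Failing to obtain a readable result bears directly on that question, but no condition in Section 7.1 looks at it:

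- The sample images are prepared in advance, so a subject's own invalid test does not enter that score.
- A subject who correctly recognises an invalid cassette is recorded as agreeing with the observer, and agreement is not a condition in any case.
- None of the 11 questionnaire items asks whether a result was obtained.

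The step score is the only route by which an invalid test can affect the verdict, and it averages eight steps. A favourable verdict could therefore be issued for a kit with which a large share of users obtained no result. The data that would show this are already collected, but no analysis or threshold is attached to them.

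**Working it through.** The plan gives no sample-size derivation, error rate or expected invalid rate, so there is no figure of its own to reproduce. The check uses the plan's counts.

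**Inputs.** 30 subjects, 15 in each user group (Synopsis); 8 critical steps and 10 images per subject (Section 3.5); 80% thresholds (Section 7.1). The minimum of 30 is taken as the actual number.

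**Pass limits, pooled.**
- Steps: 30 × 8 = 240; 0.80 × 240 = 192 needed, so 48 failures are allowed.
- Images: 30 × 10 = 300; 0.80 × 300 = 240 needed. The subject's own cassette does not enter.

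**How far the step score falls when tests are invalid.** Suppose each invalid test comes from one missed step and all other steps are correct.
- 15 of 30 invalid: (240 − 15)/240 = 225/240 = 93.75%, a pass. The valid rate is 15/30 = 50% (exact 95% interval 31% to 69%).
- 30 of 30 invalid: (240 − 30)/240 = 210/240 = 87.5%, a pass.

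With two missed steps per affected user, 24 users can be affected: (240 − 48)/240 = 192/240 = 80%, exactly at the limit. If all 30 miss two steps, the score is 180/240 = 75%, a fail.

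**Reading the 80% within each subject.** One missed step gives 7/8 = 87.5%, a pass; two give 6/8 = 75%, a fail. One decisive error per user still passes.

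**Allowing for other errors.** Assume one decisive step is done correctly with probability q, the other seven with probability r, all independently. Then P(pass) = Σₖ P[Bin(30, q) = k] × P[Bin(210, r) ≥ 192 − k].
- q = 0.5: 0.99 for r = 0.90; above 0.999 for r = 0.95.
- q = 0.3: 0.90 for r = 0.90; above 0.999 for r = 0.95.

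**Behaviour of a condition on valid first tests at 24 of 30.** 24/30 = 80%, exact 95% interval 61% to 92%. The chance of meeting it, P[Bin(30, p) ≥ 24], is:

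| True valid rate p | 50% | 70% | 80% | 90% | 95% |
|---|---|---|---|---|---|
| Chance | 0.001 | 0.16 | 0.61 | 0.97 | 0.999 |

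**Which attempt counts, if a repeat were done.** With an assumed 20% invalid rate per independent attempt, the valid rate is 1 − 0.20 = 80% on the first attempt and 1 − 0.20² = 96% after one repeat. At an assumed 30% it is 70% and 1 − 0.30² = 91%.

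**The case against.** The strongest reply is that the plan already measures what matters. Section 1.9 defines critical steps as those whose faulty performance could make the result inaccurate. The actions closest to volume and wicking (fitting the lid, adding three drops, leaving the cassette still) are all scored. A user-caused invalid test should therefore usually lower the step score. This stands in part: it would be wrong to infer that invalid tests leave the conditions untouched. It does not close the gap, because one decisive error in eight steps still passes.

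The control line is also narrower than it may appear. By Section 1.5 it reflects volume and wicking; nothing there says that it verifies swabbing, swab rotation or reading time. An invalid test with every step correct would point to the device. This stands, and it is why the step record should accompany each invalid test.

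Two of the ten images are invalid results, and Section 7.1 lets questionnaires and observer notes lead to changes in the instructions. Invalid tests would thus be seen and could prompt action. But recognising an invalid image is not the same as producing a valid test, and no trigger is tied to invalid results.

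A reader might also infer that failed tests will be repeated and that a practised second attempt will replace the first. The documents do not support this. The repeat wording is in the device description, the procedure gives one kit and one pass, and each cartridge is labelled and photographed, so a repeat would leave a trace. Only a need for clarification remains.

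Finally, the 80% level is borrowed from pooled step and image scores, with no separate rationale for valid tests. It tolerates 6 invalid tests in 30, and a kit with a true valid rate of 80% meets it about 61% of the time. That is a fair limit on what the added condition can establish.

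**Conclusion.** The concern holds as a gap in the decision rule and the analysis, not in data capture. No condition in Section 7.1 uses the subject's own test outcome, and any number of invalid tests from 0 to 30 is compatible with a favourable verdict. In the extreme case, 30 invalid tests from one missed step each still give a step score of 87.5% against the required 80%.

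This rests on 30 subjects, the eight listed steps, and an 80% threshold read as pooled or within subject. If the threshold applied to each step separately, which the text does not say, a step missed by more than 6 of 30 users would fail.

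A reader might go further and conclude that users will often fail to obtain a result. The documents give no invalid rate, so the finding concerns what the rule permits. The pass probabilities above depend on assumed step success rates and independence.

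**What to change.** In Section 7.1:

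- Report the number and percentage of subjects with a valid first test, with an exact 95% confidence interval, overall and separately for the 15 self-testers and the 15 who test a child.
- Add a fourth condition for the favourable verdict: at least 80% of subjects (24 of 30) obtain a valid first test. State alongside it that 24 of 30 has an exact lower limit of about 61%.
- List the observer's step record for each invalid test, so that user errors can be told apart from possible device failures.

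As a clarification, reconcile the repeat wording in Section 1.5 with the single-test procedure in Sections 1.9 and 3.5. State in Section 3.5 that the first attempt is the one scored for steps and interpretation, and that any repeat is recorded separately.

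The cost is a few sentences and one tabulation from cassettes that are already read and photographed, with no new subjects or procedures. The downside is one more condition that the kit must meet.

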#### 1.5.1 Intended Use

The MGC Health COVID-19 & Flu A+B Home Multi Test is a lateral flow immunochromatographic antibody assay intended for the simultaneous qualitative detection and differentiation of the nucleocapsid antigen from SARS-CoV-2, influenza A and/or influenza B directly from anterior nasal swab specimens obtained from individuals, who are suspected of respiratory viral infection within five (5) days of symptom onset. This test is intended for nonprescription home use with self-collected direct anterior nares swab samples from individuals ages 14 years and older or adult lay user collected anterior nares swab samples from individuals aged 2 to 13 years.

Results are for the simultaneous identification of SARS-CoV-2, influenza A, and influenza B. The MGC Health COVID-19 & Flu A+B Home Multi Test is not intended to detect influenza C antigens. These viral antigens are generally detectable in anterior nasal swab specimens during the acute phase of infection. Positive results indicate the presence of viral antigens, but clinical correlation with patient history and other diagnostic information is necessary to determine infection status. Positive results do not rule out bacterial infection or co-infection with other viruses. The agent detected may not be the definite cause of disease. Individuals who test positive with the MGC Health COVID-19 & Flu A+B Home Multi Test should self- isolate and seek follow-up care with their physician or healthcare provider as additional testing may be necessary.

Negative SARS-CoV-2 results should be treated as presumptive and confirmed with a molecular assay, if necessary, for patient management. Negative results do not rule out SARS-CoV-2 infection and should not be used as the sole basis for treatment or patient management decisions, including infection control decisions. Negative results should be considered in the context of an individual's recent exposures, history, and the presence of clinical signs and symptoms consistent with COVID-19.

Negative influenza A and B test results should be treated as presumptive. It is recommended these results be confirmed by viral culture or an FDA cleared influenza A and B molecular assay. Negative results do not preclude influenza virus infection and should not be used as the sole basis for treatment or other management decisions.

Additional confirmatory testing with a molecular test for positive results may also be necessary, if there is a low likelihood of COVID-19 or influenza, such as in individuals without known exposures to COVID-19 or influenza or residing in communities with low prevalence of these infections. Individuals who test negative and continue to experience symptoms of fever, cough and/or shortness of breath may still have SARS-CoV-2 or influenza and should seek follow-up care from their healthcare provider. Individuals should provide all results obtained with this product to their healthcare provider for public health reporting. All healthcare providers will report all test results they receive from individuals who use the authorized product to relevant public health authorities in accordance with local, state, and federal requirements using appropriate LOINC and SNOMED codes, as defined by the Laboratory In Vitro Diagnostics (LIVD) Test Code Mapping for SARS-CoV-2 Tests provided by the CDC.

Confidential

